### Clinical Data to be Collected

**The following clinical data points will be collected and recorded in REDCAP (Please see attached data sheet):**

- Age
- Birth Gender
- Original Cancer Stage
- Date of original diagnosis
- Cancer Location
- Cancer Stage
- HPV Status
- Cancer Treatment (choice=Surgery)
- Cancer Treatment (choice=Chemotherapy)
- Cancer Treatment (choice=Radiation)
- Surgery Date
- Radiation Dosage
- Chemotherapy Type/Dosage
- Chemotherapy treatment range
- Date of Completion of Initial Treatment
- Smoking Pack Year History
- Date of Study MRI
- Why enrolled?
- MRI Imaging uploaded
- Biopsy Obtained
- Pathology confirms recurrence
- Date of recurrence diagnosis
- Length of time from MRI to clinical/radiographic progression
- Last clinical F/U
- Last imaging F/U
- Treatment after repeat biopsy/surgery

**Duration of Imaging:** MRI data to include anatomical MPRAGE volumetric T1, fat-saturated T2-weighted image (for anatomical localization and cystic/necrotic changes) and optimized research DWI sequence will be acquired in 30 minutes. If at any time the constraints of this protocol are considered detrimental to the patient's health and/or the patient no longer wishes to continue

imaging, the protocol should be discontinued and the reason(s) for discontinuation documented in the case report forms.

**Post-imaging:** While there are no anticipated problems during the research imaging, continuous monitoring for any adverse events or abnormal events will occur during imaging. Once the research MRI is complete, the subject will be asked by a member of the study team how they are feeling prior to leaving the CCIR. If for any reason, the subject is feeling abnormal, [name] or [name], the on-site neuroradiologist, will be notified and will address any adverse events.

**Patient Compensation:** Subject will receive \$100 at the completion of their research DWI MRI imaging. Subjects will be provided compensation by check.

## **IMAGE ARCHIVING**

Our image cloud computer system is the CNDA archive maintained at the Washington University School of Medicine, and it will serve as a central repository for all data collected as part of this project. Data will be securely transferred from the scanning facilities to CNDA. CNDA data are anonymized and can be accessed remotely.

## **MRI PROCESSING GUIDELINES**

**Overview:** All MRI studies will be blindly evaluated by at least two experienced neuroradiologists (Drs. [name] and [name]). If there is an urgent or emergent finding obtained by the research MRI study, this will be communicated by one of the neuroradiologists directly to the ENT physician for follow up who is caring for the patient, as per normal departmental protocol. In the case of this study, incidental findings are defined as anything not already noted in the medical record.

**Methodology of MRI Evaluation:** The research MRI study of the head and neck will be performed on a Siemens 3T MRI Scanner system located in the Center for Clinical Imaging Research (CCIR). Multiplanar / multisequence MRI data including the optimized research DWI sequence will be acquired. MRI subjects must complete an MRI screening evaluation form before entering MRI zone 3 or the scanning room. Images will be anonymized and sent to CNDA for archiving after diagnostic reports are complete. All anonymized MRI studies will then be blindly evaluated by at least two experienced neuroradiologists (Drs. [name] and [name]). MUSE image processing will be applied post-acquisition.

**Methodology of ADC Evaluation:** The primary tumor, suspicious lesion, and/or area of post-treatment change will be first identified in the anatomical images and then outlined in the ADC sequence by experienced neuroradiologists (Drs. [name] and [name]), excluding areas of cystic change and necrosis. If there are multiple lesions, only the dominant lesion with the lowest ADC will be utilized for analysis, akin to RECIST criteria. If there is geometric distortion, a region of interest will be placed in the undistorted region only. A histogram analysis method will be used to examine the distribution of ADC values within each region of interest (ROI). Only measurable disease defined as a primary tumor, a suspicious lesion, and/or an area of post-treatment change measuring at least 0.5 cm in two perpendicular dimensions will be used. Technically poor or non-diagnostic MR images will be excluded. ADCmean/min will be computed.

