## 2.0 OBJECTIVES

The Specific Aim of this application is as follows: To compare SUVmax and ADCmean/min values to assess the capability of the new DWI pulse sequence to differentiate post-treatment change from residual or early recurrent tumor.

Hypothesis: The optimized research DWI pulse sequence obtained up to 3 weeks post treatment will accurately identify residual/recurrent tumor, as confirmed by the clinical FDG PET/CT obtained at 3-6 months. This would potentially result in a modification of imaging follow-up algorithms, increased cost-savings and eliminate radiation exposure to patients inherent in PET/CT. This would also result in earlier changes to treatment regimens and stratify patients into more or less aggressive tumor response to treatment. The gold-standard will be histological tissue where available and/or 1-year clinical and imaging outcomes, including imaging outcome measurements such as RECIST 1.1 [De Bree, 2017], PERCIST [Joo Hyun, 2016] and iRECIST [Persigehl, 2020].

**Figure 1:** DWI data obtained from a healthy volunteer with a GE 3 Tesla system and eight-channel neurovascular array coil. Single-shot EPI-based DWI was obtained: matrix size = 128  $\times$  128; parallel imaging acceleration factor = 2; field of view = 24 cm  $\times$  24 cm; b-value = 1000 s/mm^2. B, High-resolution DWI data obtained with four-shot interleaved EPI pulse sequence (matrix size = 256  $\times$  256; field of view = 24 cm  $\times$  24 cm; b-value = 1000 s/mm^2) and reconstructed with our developed MUSE algorithm.

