## **4.0 STUDY PROCEDURES**

### **IMAGING PLAN**

Overview: 60 biopsy-proven neck SCC patients after treatment with surgery, radiation or chemo-radiation will be enrolled for this trial. The Otolaryngology, Head and Neck Surgery physicians and their clinic staff will assist in coordinating enrollment. The patients will undergo an optimized research neck DWI MRI, up to 3 weeks post-treatment and then a standard-of-care 3-6 months post-treatment FDG PET/CT examination. (\*\*Note: Patients who do not undergo SOC PET/CT at the 3-6 month time point will be considered inevaluable and will be replaced.) Patients who sign the consent form but do not have the MRI will not be considered accrued on this study. The optimized DWI images will be acquired on a dedicated research Siemens 3T Scanner belonging to Washington University's Center for Clinical Imaging Research. The standard-of-care FDG PET/CT mages will be acquired at one of the Siemens Biograph clinical PET/CT units located throughout the Barnes-Jewish Hospital Systems. We will compare the ADC values (ADCmin and ADCmean) to the optimized DWI sequence to FDG PET

SUVmax. For up to 1 year post-treatment, patients' medical records will be reviewed after scheduled SOC visits to additionally assess for clinical outcomes.

	Baseline	up to 3 Weeks Post-Treatment	3-6 Months Post-Treatment	Follow up for up to 1 year post-treatment
Screening	X			
Enrollment	X			
Medical Record Review	X	X	X	X
DWI MRI		X		
FDG PET/CT			SOC	

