## **5.9 Incidental Findings**

The research MRI scan is not a clinical MRI examination and is not conducted to diagnose brain abnormalities. However, some of the sequences are similar to clinical tests, and these images are reviewed for incidental findings by a board-certified radiologist. If there is an incidental observation from the testing which may be clinically significant, such as a suspected tumor or aneurysm, the Principal Investigator will communicate this information to the treating physician for review; this includes incidental finding of new tumor. If indicated, the Principal Investigator will contact the participant with this information. With your permission your doctor may also be contacted so that follow-up may occur as appropriate.\*

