## 7.0 STATISTICAL CONSIDERATION

### STATISTICAL ANALYSIS

Study Design and Endpoints: This is a pilot study designed as a paired, prospective, single-blinded study in which we compare the sensitivity and specificity of the optimized DWI sequence ADCmean/min versus FDG PET/CT SUVmax for the evaluation of recurrent SCC in post-treatment patients. The primary endpoints of sensitivity and specificity will evaluate the diagnostic accuracy of the optimized DWI sequence ADCmean/min versus the standard-of-care FDG PET/CT SUVmax. The secondary endpoint will evaluate if the enhanced DWI sequence can more expediently assess non-responders to treatment as compared to FDG PET/CT.

Aim 1: The 60 subject sample size for this pilot study was chosen for feasibility of recruitment based on the approximately 650 PET/CT exams performed for head and neck tumor in 2018. ROI will be used for statistical assessments of ADC measurements (see methodology of ADC measurement, above). FDG-PET SUVmax results will be used as the reference standard for tumor or non-tumor tissue. ADCmean, ADCmin and standard deviation will be used to describe distribution of ADC measurements (AADC) in tumor and non-tumor tissues and independent sample t-test will be used to compare ADC measurements between the two groups. Mean difference and 95% confidence interval around that will be used to interpret our results. For ROC analysis, the area under the curve (AUC) will be calculated and the Youden's J index will be used to identify the value of the predictor variable that optimized sensitivity and specificity. Youden's J index varies from 0-1. The threshold value that provides the value of the J index closer to 1 is the value with the best performance and discriminative power. PPV and NPV will also be evaluated. The logistic regression model allows for evaluating this impact after controlling for potential confounders. We will explore the linearity assumption of relationship of delta ADC with logit of outcome (response to treatment) and if the assumption is violated,

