polynomial effects will be explored, and data transformation will be employed as needed. All statistical analysis will be carried out by [name], a biostatistician in the ENT Department with extensive experience in head and neck cancer research. A 90% confidence interval will be calculated for the differences in sensitivity and specificity of the enhanced DWI sequence ADCmean/min as compared with the standard-of-care FDG PET/CT SUVmax. The positive and negative predictive values will also be evaluated. Since this is a pilot study, no existing data can be utilized to calculate a power analysis.

A binary logistic regression model will be utilized to evaluate the impact of the change in ADC in predicting early non-responders to treatment. A p-value will be calculated to evaluate if the enhanced DWI sequence can more expediently identify non-responders to treatment as compared to FDG PET/CT.

(\*\*Note: Patients who do not undergo SOC PET/CT at the 3-6 month time point will be considered inevaluable and will be replaced.)

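### A tumor seen on the research MRI can be treated before the 3-6 month PET, and the plan has no rule for scoring DWI or PET in that patient

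*Combined protocol and SAP*

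**What the plan says.** **Timing.** Section 4.0, Imaging Plan: "The patients will undergo an optimized research neck DWI MRI, up to 3 weeks post-treatment and then a standard-of-care 3-6 months post-treatment FDG PET/CT examination".

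**Disclosure.** Two places deal with findings on the research scan. In the MRI Processing Guidelines, an urgent or emergent finding triggers a report: "this will be communicated by one of the neuroradiologists directly to the ENT physician for follow up". The same paragraph defines an incidental finding as anything the medical record does not already contain. Section 5.9 gives suspected tumor as an example of a clinically significant observation and states that "the Principal Investigator will communicate this information to the treating physician for review; this includes incidental finding of new tumor".

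**Data collected.** The REDCap list in Section 4.0 includes biopsy, pathology-confirmed recurrence, date of recurrence diagnosis and "Treatment after repeat biopsy/surgery".

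**Reference standard.** Section 7.0 takes FDG-PET SUVmax as the reference for tumor versus non-tumor tissue. The hypothesis in Section 2.0 is that early DWI "will accurately identify residual/recurrent tumor, as confirmed by the clinical FDG PET/CT obtained at 3-6 months", but the same paragraph names histology where available and/or 1-year outcomes as the gold standard. The PET/CT processing guidelines measure SUVmax in the region of interest copied from the earlier MRI.

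**Missing PET.** Sections 4.0 and 7.0 treat a patient without the 3-6 month PET/CT as inevaluable and replace that patient.

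**Primary comparison.** Section 7.0: "A 90% confidence interval will be calculated for the differences in sensitivity and specificity" of DWI and PET. Neither Section 7.0 nor any other section says how to classify a patient treated between the two scans.

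**The concern.** The index test can change what the later test measures. If a DWI finding leads to biopsy and successful treatment, the tissue that DWI flagged is no longer there when SUVmax is read in the copied region. The patient is then handled in one of three ways:

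- **PET as reference:** a true DWI detection is scored as a false positive.
- **Histology as reference:** DWI is scored correctly, but a PET done after the tumor was treated is scored as a miss.
- **No 3-6 month PET:** the patient is replaced. The patients lost by this route are DWI true positives.

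The first and third routes work against DWI and the second works in its favor. The primary sensitivity and specificity results can therefore move in either direction according to which section of the protocol the analyst follows. The affected patients are also the ones who matter most to the secondary endpoint, early identification of non-responders.

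**Working it through.** **1. Is there time?** Taking 3 months as about 13 weeks and 6 months as about 26, the interval between scans is at least 13 - 3 = 10 weeks and at most about 26 weeks.

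**2. The plan's own figures.** The only design number is 60 patients: "The 60 subject sample size for this pilot study was chosen for feasibility of recruitment". The plan adds: "Since this is a pilot study, no existing data can be utilized to calculate a power analysis". It states no prevalence, accuracy or rate of early treatment, so there is no figure to reproduce, and every input below other than 60 is an assumption.

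**3. Inputs for the illustration.** 60 patients, 18 with tumor at MRI and 42 without; DWI sensitivity and specificity 85%; PET sensitivity 80% and specificity 100%; the two tests independent given disease. A share f of DWI-detected tumors is treated so that the copied region is PET-negative.

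- DWI true positives 0.85 × 18 = 15.3; false negatives 2.7
- DWI true negatives 0.85 × 42 = 35.7; false positives 6.3; all DWI positives 21.6
- Cleared before PET: m = 15.3f

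**4. PET as reference.**

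- PET+ and DWI+: 0.8(15.3 - m)
- PET+ and DWI-: 0.8 × 2.7 = 2.16
- PET- and DWI-: 35.7 + 0.2 × 2.7 = 36.24
- Apparent specificity = 36.24 / (60 - all PET+)
- Apparent PPV = 0.8(15.3 - m) / 21.6
- Apparent sensitivity = 0.8(15.3 - m) / [0.8(15.3 - m) + 2.16]

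| f | m | PET+ | DWI specificity | DWI PPV | DWI sensitivity |
|---|---|---|---|---|---|
| 0 | 0 | 14.40 | 79.5% | 56.7% | 85.0% |
| 10% | 1.5 | 13.18 | 77.4% | 51.0% | 83.6% |
| 25% | 3.8 | 11.34 | 74.5% | 42.5% | 81.0% |
| 50% | 7.7 | 8.28 | 70.1% | 28.3% | 73.9% |

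The f = 0 row is already below the assumed 85% specificity because PET misses 20% of tumors. Only the change down each column is due to treatment between scans.

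**5. Histology as reference.** DWI sensitivity stays at 85%. Apparent PET sensitivity is 0.8(18 - m)/18, assuming that treatment is unrelated to whether PET would have been positive.

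| f | PET sensitivity | DWI minus PET |
|---|---|---|
| 0 | 80.0% | +5 points |
| 10% | 73.2% | +12 |
| 25% | 63.0% | +22 |
| 50% | 46.0% | +39 |

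With other assumed accuracies (DWI 80%, PET 90%), the difference starts at -10 points. At f = 25%, PET sensitivity is 0.90 × (1 - 0.25 × 0.80) = 72% and the difference becomes +8, so the ranking of the two tests reverses.

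**6. Patients without a PET.** If the m treated patients are removed, DWI sensitivity among the remaining patients is (15.3 - m)/(18 - m): 81% at f = 25% and 74% at f = 50%. Against PET at 80%, the difference falls from +5 to +1 and -6 points. Leaving treated patients out of the paired comparison has the same effect, because omission removes only DWI true positives.

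**7. Bounds.** Count the m patients once as PET-positive, giving PET sensitivity [0.8(18 - m) + m]/18, and once as PET-negative, as in step 5. At f = 25% this gives 84.3% and 63.0%, so DWI minus PET lies between +0.8 and +22 points. At f = 50% it gives 88.5% and 46.0%, or -3.5 to +39 points. Both ranges contain the assumed true +5.

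**The case against.** **Disclosure.** The sentence in the MRI Processing Guidelines is limited to urgent or emergent findings. A reader might infer that it alone sends every suspected tumor to the treating physician; it does not. The support is Section 5.9 read with the definition of an incidental finding. Section 5.9 speaks of incidental observations, so applying it to the study's target lesion is an interpretation. It is a natural one, because suspected tumor and new tumor are both named.

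**Expectation of early treatment.** A reader might also infer from the REDCap fields that treatment before PET is expected. Follow-up runs to 1 year, and the same fields could record treatment after a positive PET. The documents show that early treatment is possible, not that it is planned or common.

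**Size.** Starting from 85% specificity and 71% PPV would treat PET as error-free, which contradicts an assumed PET sensitivity of 80%. That calculation gives specificity losses of 7 and 13 points at 25% and 50% cleared; the consistent calculation gives 5 and 9. For PPV the losses are 14 and 28 points, not 18 and 35. PPV is also not a primary endpoint.

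**Link to the reference-standard conflict.** The DWI false positive arises only if PET is the reference. In that case a DWI-PET accuracy difference has no useful meaning even without early treatment, because PET is correct by definition. This stands, but resolving the conflict does not remove the problem: PET alone mis-scores DWI, and histology alone mis-scores PET.

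**Pilot status.** With 60 patients and no power calculation, wide uncertainty is accepted. That bears on precision, not on a systematic misclassification whose direction depends on a choice left open.

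**Conclusion.** The concern holds as a gap in the analysis rules. When followed, the PET-reference rule and the replacement rule give a wrong classification, or lose the patient, whenever a tumor found by DWI is proven by tissue and cleared before PET. Under the stated assumptions, 25% cleared (about 4 of 60 patients) costs about 5 points of apparent DWI specificity with PET as reference, or 17 points of apparent PET sensitivity with histology as reference. At 50% cleared the losses are about 9 and 34 points.

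The frequency is unknown and could be close to zero, in which case the effect is negligible. A cleared tumor is also assumed to read PET-negative, which need not always hold: Section 1.0 itself notes false-positive FDG uptake with inflammation.

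Two stronger conclusions are not supported. A reader might infer that the primary comparison cannot be interpreted at all, but that would need evidence that early treatment is frequent, and the documents give none. A reader might also infer that telling the treating physician is the fault. It is not; only the scoring needs a rule.

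**What to change.** Leave disclosure and patient care unchanged. Add to Section 7.0, before outcome data are examined:

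1. If new anticancer treatment for suspected residual or recurrent disease is given between the research MRI and the PET, disease status for DWI sensitivity and specificity is the tissue result obtained before or at that treatment, not the later SUVmax.
2. These patients stay in the DWI accuracy analysis even without a 3-6 month PET. For that analysis they are exempt from the rule that makes a patient inevaluable and replaced. Amend the matching note in Section 4.0.
3. The post-treatment PET is not scored as a PET miss. The paired DWI-PET difference is reported as bounds, counting these patients once as PET-positive and once as PET-negative. A version that omits them is a sensitivity analysis only, because of the selection shown in step 6.

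Add one REDCap yes/no field for biopsy or treatment prompted by the research MRI, and report the count beside the primary results.

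The cost is a short paragraph, an amended note and one data field; biopsy, pathology, recurrence date and later treatment are already collected. The downside is a slightly longer analysis and a wider reported range for the paired difference.

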## 1.0 BACKGROUND AND RATIONALE

Head and neck tumors can be a significant imaging diagnostic challenge. Anatomic imaging alone is insufficient to differentiate between post-treatment change and recurrent tumor, as both demonstrate increased T2/FLAIR signal and enhancement. Diffusion-weighted sequences (DWI) is a more sensitive and specific sequence that can be used to evaluate this tumor, and that can more easily differentiate between residual/recurrent tumor and post-treatment change (Vandecaveye, 2007). Metabolic imaging with FDG PET/CT is impacted by false-positives in the setting of inflammation or post-radiation necrosis and thus, data must be acquired 8-12 weeks post-treatment to avoid this pitfall. Moreover, PET/CT imaging is less available compared to MRI or CT. MRI does not require ionizing radiation, which is an important factor in head and neck squamous cell cancer patients, as they have an increased risk of secondary tumors such as lung cancer.

MRI systems that include diffusion-weighted imaging (DWI) and apparent diffusion coefficient (ADC) measurements hold promise to facilitate differentiation of tumor recurrence from post-treatment changes and associated complications, since areas of tumor demonstrate restricted diffusion and post-treatment changes do not [Chawla, 2009; Friedrich, 2008; Hermans, 2010; Jansen 2010; King, 2010 and 2013; Maeda, 2008; Mudana, 2018; Perrone, 2011; Vandecaveye, 2007 and 2010]. However, there are multiple pitfalls associated with conventional DWI related to artifacts such as fat saturation, distortion, aliasing/ghosting and spatial resolution. These limit the utility of this technique.

We propose a longitudinal study evaluating post-treatment changes in patients with squamous cell carcinoma (SCC) of the neck using an **innovative optimized DWI pulse sequence to identify more accurately recurrent tumors as well as early non-responders to therapy**.

[figure not shown]

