## PET/CT IMAGING PROCESSING GUIDELINES

Overview: When the PET/CT is ordered as a clinical workup, a diagnostic report will be issued by the Nuclear Medicine Department faculty. Neither [name] nor [name] will participate in the preparation or issuing of this report.

Methodology of SUV Evaluation: Anonymized FDG PET/CT data from CNDA will be uploaded into a MIM workstation (MIM Software Inc., Cleveland, Ohio). Fused MPRAGE/DWI images will be used. The region of interest chosen for the evaluation of ADC values will be copied onto the FDG CT/PET, and the SUVmax will be measured. While there is significant variability in SUV measurements [Kinehan, 2010], the reported literature suggest SUVmax > 9.0 -with interquartile range (IQR) 7.4–13.9 and range of 1.5-20.1 - is diagnostic of squamous cell carcinoma [Schwartz, 2004; Morand, 2018] for the primary mass and >4.5 for nodal tumor [Paidpally, 2012]. PET/CT studies are standard of care and are reported as clinical studies.

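### SUVmax is measured inside the ADC region already trimmed for DWI distortion, so PET can inherit DWI's blind spot and the DWI-PET comparison can be biased in DWI's favour

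*Combined protocol and SAP*

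**What the plan says.** Four rules in section 4.0 act together.

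- **Locating the lesion.** The tumor, suspicious lesion or post-treatment area "will be first identified in the anatomical images and then outlined in the ADC sequence by experienced neuroradiologists".
- **Distortion.** "If there is geometric distortion, a region of interest will be placed in the undistorted region only". The text gives no minimum for what must remain, no flag and no count. The size rule, "measuring at least 0.5 cm in two perpendicular dimensions will be used", applies to the lesion or area and is not stated for the trimmed region.
- **Unusable scans.** "Technically poor or non-diagnostic MR images will be excluded". No criterion is given for this.
- **PET.** "The region of interest chosen for the evaluation of ADC values will be copied onto the FDG CT/PET, and the SUVmax will be measured".

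The list under Clinical Data to be Collected has no field for distortion or image quality. It refers to an attached data sheet that is not among the documents, so the absence is not certain.

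The statistics depend on these regions. Section 7.0 states that "FDG-PET SUVmax results will be used as the reference standard for tumor or non-tumor tissue", and it also plans a 90% confidence interval for the DWI-PET differences in sensitivity and specificity. Section 2.0 names a different gold standard: histology where available and/or 1-year clinical and imaging outcome.

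**The concern.** Section 1.0 says that "there are multiple pitfalls associated with conventional DWI related to artifacts such as fat saturation, distortion, aliasing/ghosting and spatial resolution" and presents the optimized sequence as an improvement on artifacts that should raise diagnostic accuracy. The trial should therefore show how often distortion remains and what it costs.

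The plan instead removes distorted tissue from the ADC measurement and carries the reduced region over to PET. PET does not suffer from DWI distortion, yet it is read only where DWI could be read. Tumor in the distorted part may then be seen by neither test. At stake is the main comparison, because a DWI limitation would be charged to the comparator, or to the reference standard, as well as to DWI.

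**Working it through.** The plan gives no figure to reproduce: the 60 patients were chosen for feasibility, with no power calculation.

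**Direction, without numbers.** Take the milder reading, in which the region is only trimmed within the lesion. A maximum over a subset cannot exceed the maximum over the whole, so SUVmax stays equal or falls. A minimum over a subset cannot be below the minimum over the whole, so ADCmin stays equal or rises compared with a distortion-free reading of the full lesion. Both shifts point toward no tumor. ADCmean can move either way.

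**Size under the section 2.0 gold standard.** None of these inputs is in the documents; all are assumptions.

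- Sensitivity when the region contains the tumor: DWI 0.80, PET 0.90.
- Probability of a positive call when the region holds only non-tumor tissue: DWI 0.20, PET 0.10.
- d = share of tumors lying wholly in the distorted part: 10%, 20% or 30%.

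As written, DWI = 0.80(1-d) + 0.20d and PET = 0.90(1-d) + 0.10d. With PET read over the full lesion and the ADC rule unchanged, PET = 0.90.

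| d | DWI | PET, copied region | Difference as written | PET, full lesion | Difference |
|---|---|---|---|---|---|
| 10% | 0.74 | 0.82 | -8 points | 0.90 | -16 points |
| 20% | 0.68 | 0.74 | -6 points | 0.90 | -22 points |
| 30% | 0.62 | 0.66 | -4 points | 0.90 | -28 points |

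The copied region therefore shifts the difference by d(0.90 - 0.10), that is 8, 16 and 24 points in DWI's favour. With no distortion the difference would be -10. As written, the DWI deficit appears to shrink as distortion becomes more common.

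If the wholly distorted tumors were instead all scored as DWI failures, DWI would be 0.80(1-d) = 0.72, 0.64 and 0.56, and the difference from 0.90 would be -18, -26 and -34. That adds only 2, 4 and 6 points, so most of the effect comes from the copied region and little from the scoring of the ADC reading.

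**Size under the section 7.0 SUVmax reference.** A second set of assumptions: 60 patients, 20-40% with tumor (12 to 24), DWI sensitivity and specificity 0.85 in readable tissue, and a share f of 5%, 10% or 20% of tumors wholly in distorted tissue and read as negative.

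- Independent reference: sensitivity = 0.85(1-f) = 0.8075, 0.765 and 0.680. The failure is visible.
- Excluded as non-diagnostic: sensitivity stays at 0.850.
- SUVmax in the same trimmed region, with the tumor labelled non-tumor: sensitivity stays at 0.850 and specificity rises slightly. With 12 tumors and f = 5%, 0.6 tumors are relabelled: (0.85 x 48 + 0.6)/48.6 = 0.852. With 24 tumors and f = 20%, 4.8 are relabelled: (0.85 x 36 + 4.8)/40.8 = 0.868.

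The first accounting differs from the other two by about 4 to 17 points of sensitivity.

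**Precision.** The 90% half-width for one sensitivity of 0.85 is 1.645 x sqrt(0.85 x 0.15/n): 0.170 with 12 tumors and 0.120 with 24.

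**The case against.** The strongest reply is that the distortion sentence sits within a procedure that starts from a lesion found on anatomical images. Its natural meaning is that the lesion's region is trimmed to its undistorted part. A reader might infer that the region is moved to whatever tissue happens to be undistorted; the wording is ambiguous, but the documents do not say that. The direction argument above does not need that reading.

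Other strong inferences also fail.

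- **That such a tumor is recorded as a negative.** No rule says so. The ADC cut-off comes from Youden's index and is not yet set, and tumor extending into the retained part can still read positive. A scan with the whole lesion distorted may instead be excluded as non-diagnostic.
- **That DWI's failures are always hidden.** Against histology or 1-year outcome, a missed tumor is a DWI false negative and lowers DWI sensitivity, as the table shows. What is distorted there is the comparison, because PET falls as well.
- **That distortion is DWI's main failure mode.** Section 1.0 lists it as one of four artifacts of conventional DWI, unranked.

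It is also fair that the inputs are assumed, that d counts only tumors wholly outside the retained region, and that section 1.0 reports improved artifact parameters for this sequence. Distortion may be rare. With half-widths of 12 to 17 points for a single sensitivity, a small bias could not be told from chance in this pilot. None of this removes the one-directional effect of the copied region on SUVmax, and without a record of distortion the trial could not show that the effect was small.

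**Conclusion.** The point holds as a bias built into two stated rules taken together. Followed exactly, the plan can lower SUVmax because of a DWI artifact. Under section 7.0 that can relabel tumor as non-tumor. Under section 2.0 it lowers PET sensitivity along with DWI's and, when PET is the better test, pulls their difference toward zero.

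The size cannot be obtained from the documents, which give no distortion rate, recurrence rate or ADC accuracy. The shift of 8, 16 and 24 points is illustrative and rests on the assumed sensitivities, the assumed positive rates and 10-30% of tumors lying wholly in distorted tissue; it shrinks in proportion if that share is lower. The documents do not support saying that these tumors are necessarily scored as negatives, or that DWI's failures vanish from its own accuracy under every reference. The plan should be changed, since the effect falls on the primary comparison and is cheap to prevent.

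**What to change.** 1. In Methodology of ADC Evaluation, state that the lesion is outlined in full on the anatomical images, that the ADC region is the undistorted part of that outline, and that this part must itself meet the 0.5 cm minimum in two perpendicular dimensions. Otherwise DWI is recorded as not assessable. Record for each patient whether distortion was present.
2. In Methodology of SUV Evaluation, measure SUVmax over the full anatomical outline in place of the distortion-trimmed ADC region. That section already uses fused MPRAGE/DWI images, so the anatomical image is at hand.
3. In section 7.0, report the numbers of trimmed and not-assessable cases, and add a sensitivity analysis counting not-assessable DWI as failures.

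The last item belongs in a sensitivity analysis: it is a worst-case choice that also turns tumor-free patients into false positives, so it need not be the primary rule. A required minimum share of the lesion, such as half, would be a convention and is not needed here.

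The cost is one recorded field and one extra contour, with the same scans, patients and readers. Reported DWI accuracy may be lower, and in distorted cases ADC and SUVmax will no longer come from identical regions.
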